## Summary of research scheme

Program name	Based on long-term survival outcomes of primary non-ampulla duodenal adenocarcinoma
Applicant	Nanfang Hospital of Southern Medical University
Principal investigator	[name]
Study center and director	Southern Medical University Nanfang Hospital [name]
Object of study	Duodenal adenocarcinoma (DA) patients
Objective	
Main Objective: To determine whether radical DA resection is associated with an improvement in 5-year overall survival
 
Secondary objectives: Adjuvant therapy, pancreatic invasion, and advanced tumor stage were identified as significant predictors of overall survival

Study group	Histologically confirmed non-ampulla DA (including all stages of disease at diagnosis)
Study design	Retrospective cohort study
Study duration	2024.04-2024.06
Sample size	400 cases
Inclusion criteria	
(1)At least 18 years old;
 
(2)Voluntary signing of informed consent;
 
(3)Non-ampulla DA patients were diagnosed according to the Chinese Medical Association's Clinical Diagnosis and Treatment Guidelines for Gastrointestinal Tumors (2022 edition), including patients at all stages of diagnosis;
 
(4)Unless there is no other malignant tumor diagnosed in the ampulla DA.

Exclusion criteria	
(1)Cancer of the ampulla or other forms of gastrointestinal cancer
 
(2)Incomplete medical records
 
(3)Missing diagnostic or therapeutic data
 
(4)Follow-up was lost shortly after diagnosis

Efficiency analysis	
Primary outcome measures for effectiveness analysis: median overall survival, 3 - and 5-year overall survival rates in the cohort
 
Secondary outcome measures for effectiveness analysis: Overall survival with adjuvant therapy, pancreatic invasion, and advanced tumor

Statistic analysis	
Statistical analysis
 
Rigorous statistical methods were used to analyze the collected data. Survival outcomes, including OS and DFS, were calculated from the date of diagnosis until the date of death or last follow-up, and from the date of diagnosis until the date of disease recurrence or last follow-up of DFS. Kaplan-Meier survival curves were generated to illustrate survival trends over time, and log-rank tests were used to compare the distribution of survival among different patient subgroups. Cox proportional hazard models were used to identify independent prognostic factors affecting survival. Variables considered in the model included demographic factors (age, sex), clinical features (BMI, jaundice, bleeding, anemia), preoperative laboratory values, treatment details (radical resection, adjuvant therapy), and pathological findings (AJCC stage, tumor differentiation and lymph node involvement rate). Hazard ratios (HRs) and 95% confidence intervals (CI) were calculated to estimate the strength of the association between each variable and survival outcomes.

Follow-up visit	The patients included in this study were from a hospital cohort that included cases diagnosed and treated in the Department of General Surgery at Nanfang Hospital of Southern Medical University. Inclusion criteria were histologically confirmed non-ampulla DA, including all stages of disease at diagnosis. Patients were excluded if they had ampulla cancer or other forms of gastrointestinal cancer, had incomplete medical records, or lost follow-up shortly after diagnosis.
Statistical approach	Statistical methods SPSS 25.0 and Prism 8.0.1 software were used for all statistical analyses.
Expected progress	Expected progress: From April 2024 to May 2024, data collection, sorting and analysis will be completed. From May 2024 to June 2024, monograph writing, submission and conclusion will be completed

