The treatment of DA faces several challenges, including the lack of established guidelines based on worldwide scientific evidence, the difficulty of early detection due to the rarity of the disease and the lack of specific screening markers, and the limited evidence supporting various treatment modalities. Surgical resection is the only possible treatment for DA. The complexity of surgery, which often includes pancreaticoduodenectomy, has evolved over the years, and advances in perioperative care and surgical techniques have helped reduce morbidity and mortality, but there has been no uniform improvement in long-term survival outcomes. Adjuvant therapy, including chemotherapy and radiotherapy, has been explored as a means of improving survival, especially in cases with adverse pathological features, such as lymph node involvement or the advanced stage of diagnosis. Despite these reasons, the efficacy of adjuvant therapy for DA remains controversial. There have been no randomized controlled trials comparing the efficacy of single surgery with perioperative adjuvant treatment for DA. All of the studies were retrospective comparisons of the outcomes of surgery alone and combined surgery, so there may be selection bias in patients. Numerous meta-analyses and systematic reviews have investigated the treatment of DA in depth, but most studies have been retrospective, single-center, and small-sample size series, especially in China. To address this knowledge gap, we conducted a hospital-based cohort study designed to investigate long-

term outcomes in patients with DA and to disaggregate the effects of tumor characteristics, surgery, and adjuvant therapy on survival outcomes.

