## **2. Study purpose**

2.1 Main Objectives: Whether radical DA resection is associated with improvement in 5-year overall survival

2.2 Secondary objectives: Adjuvant therapy, pancreatic invasion, and advanced tumor stage were identified as significant predictors of overall survival

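### Adjuvant survival is timed from diagnosis with no landmark or time-dependent coding, so the secondary adjuvant comparison credits immortal time to treatment

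*Combined protocol and SAP*

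**What the plan says.** The statistical analysis entry in the Summary of research scheme sets the clock: "Survival outcomes, including OS and DFS, were calculated from the date of diagnosis until the date of death or last follow-up". DFS has the same origin and runs "from the date of diagnosis until the date of disease recurrence or last follow-up of DFS".

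The same entry lists the Cox covariates. Beside age, sex, BMI, laboratory values and AJCC stage stand "treatment details (radical resection, adjuvant therapy". For the unadjusted comparison, "log-rank tests were used to compare the distribution of survival among different patient subgroups".

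Section 2.2 names the adjuvant question as a secondary objective, worded as a finding: "Adjuvant therapy, pancreatic invasion, and advanced tumor stage were identified as significant predictors of overall survival". Section 3.2 makes OS with adjuvant therapy a secondary endpoint.

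Section 10 adds descriptive tests, software and a two-sided 0.05 level. Neither document part mentions a landmark, a time-dependent covariate, an origin at surgery, or restriction of the adjuvant comparison to resected patients. Section 6.4 lists treatment modality and survival time among the data to collect, but names no date of surgery or of first adjuvant treatment. Section 1 speaks of trials "comparing the efficacy of single surgery with perioperative adjuvant treatment for DA", and nothing says whether adjuvant means postoperative treatment only.

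**The concern.** A patient can be classed as having received postoperative adjuvant therapy only after surviving diagnosis, surgery and recovery. If groups are formed by ever/never treatment and followed from diagnosis, the waiting time counts as treated survival, and everyone who dies while waiting counts as untreated. For DFS the same applies to early recurrence.

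This is misallocated person-time, not a difference in case mix, so stage and resection in the Cox model do not correct it. Kaplan-Meier curves and log-rank tests from diagnosis share the fault whatever the Cox coding.

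Section 1 calls the efficacy of adjuvant therapy unsettled and sets out to separate its effect from those of tumor and surgery. An HR that falls below 1 with no true effect cannot do that.

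**Working it through.** The plan gives no figure on this point to reproduce. It supplies n = 400, the 2009-2023 window and two-sided 0.05. Lags, treated shares and survival are not given, so every input below beyond those three is an assumption.

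**1. The mechanism by hand.** Assume exponential OS with median 24 months, no treatment effect, follow-up to 60 months, 200 of 400 patients intended for adjuvant therapy, and start at month 4. The hazard is ln 2/24 = 0.02888 per month in everyone.

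- Intended, dead before month 4: 200 × (1 − 2^(−4/24)) = 21.82. Started: 178.18.
- Started: deaths by month 60 = 178.18 × (1 − 2^(−56/24)) = 142.82. Person-months after start = 142.82/0.02888 = 4,945.2. Waiting time = 178.18 × 4 = 712.7.
- Never intended: deaths = 200 × (1 − 2^(−60/24)) = 164.64, person-months 5,700.8.
- Early deaths among the intended: 21.82/0.02888 − 712.7 = 42.8 person-months.

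Ever/never from diagnosis:
- treated rate = 142.82/(4,945.2 + 712.7) = 0.02524
- untreated rate = (164.64 + 21.82)/(5,700.8 + 42.8) = 0.03246
- ratio = 0.78

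Moving the 712.7 waiting months to the untreated side gives 142.82/4,945.2 = 0.02888 and 186.46/6,456.3 = 0.02888, ratio 1.00. A simulation of the same setting (start mean 4 months, SD 1) gave HR 0.78 with ever/never coding, and 1.00 with either time-dependent coding or a landmark. This case has no stage or resection in the model, so it shows the mechanism, not the likely size.

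**2. The planned model, with stage and resection.** Assumed for stages I/II/III/IV:
- share of cohort 10/25/40/25%
- median OS 96/60/30/10 months
- resected 95/95/80/15%
- adjuvant among resected 10/40/65/70%

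Surgery is 0.5-2 months after diagnosis, or at diagnosis for half or all of the resections. Censoring is in April 2024. True HRs are 1.0.

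| Adjuvant OS analysis | HR | False positives |
|---|---|---|
| Ever/never, start 1-3 months after surgery | 0.86-0.87 | 13-17% |
| Ever/never, start 2-4 months after surgery | 0.82 | 23% |
| As the 1-3 month case, half of untreated deaths before 3 months missing | 0.92 | 8% |
| As the 1-3 month case, all of those deaths missing | 0.97 | 6% |
| Landmark 2, 3 or 4 months after surgery (starts 1-3 months) | 0.99-1.00 | 4-6% |
| Adjuvant and resection both time-dependent | 0.99-1.00 | 4-5% |

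Repeat runs with separate code gave 0.88-0.89 (11-13%) for starts at 1-3 months and 0.82-0.83 (22-23%) for 2-4 months.

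**3. Direction once confounding is present.** In the same null cohorts, leaving stage out of the model among resected patients gives an adjuvant HR of 1.25, because sicker patients are treated more often. The two biases pull in opposite directions.

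**The case against.** **The coding is inferred.** The plan lists variables without saying how they are coded. That stands as a caveat. Ever/never remains the natural reading, because adjuvant therapy sits among baseline covariates and no other method is named.

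**Early deaths may not be in the data.** Sections 5.2, 6 and 6.1 require signed consent before data collection. Read literally, that could remove the deaths that create the bias, and the HR then moves to 0.92-0.97. This limits the size. It is a separate selection problem and not a remedy.

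**The missing dates.** A reader might infer from section 6.4 that the analysis cannot be repaired. The list is not exhaustive: it also omits the dates of diagnosis and death, which the survival definitions need. Surgery and start dates may well be in the routine records.

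**A falsely favourable result.** A reader might infer that the study is bound to report a spurious benefit. Section 1 says adjuvant therapy was explored "especially in cases with adverse pathological features, such as lymph node involvement or the advanced stage of diagnosis", and such confounding works against treatment. Only the immortal-time component has a known direction.

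**DFS.** The same cohorts give an HR of 0.82-0.83 for recurrence or death. That is not DFS as the plan defines it, which ends at recurrence or last follow-up, so the figure should not be attached to it. A recurrence-only run was still biased.

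**The main objective.** A reader might extend the point to the question "Whether radical DA resection is associated with improvement in 5-year overall survival". Resection carries immortal time only where surgery follows diagnosis, and the date of diagnosis is undefined. In the planned model the null resection HR is 0.91, 1.00 or 1.10 when 0, 50 or 100% of resections coincide with diagnosis. A separate calculation without stage (70% resected, mean lag 1.25 months, median OS 12 to 48 months) puts the spurious 5-year difference at only 0.67 to 2.45 points. This does not justify rebuilding the main analysis.

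**Conclusion.** The concern holds for the secondary adjuvant OS comparison and should be fixed. As the plan reads, treated patients are credited with time during which they could not have died as treated patients, and the listed adjustments do not remove it.

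If early deaths are in the data, and under the assumed stage mix, survival and lags, a null effect would appear as an HR of about 0.87 or 0.82, with a false-positive rate of 13-17% or 22-23% instead of 5%. With early untreated deaths partly or wholly absent it is 0.92-0.97. The mechanism is certain if adjuvant means postoperative treatment coded ever/never. The size is illustrative, and the net direction after confounding is unknown. DFS shares the mechanism, without a figure for the plan's own definition.

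The primary endpoints, whole-cohort median, 3-year and 5-year OS, involve no treatment grouping and are unaffected. This is therefore not a defect that invalidates the study.

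**What to change.** 1. State whether adjuvant therapy means postoperative treatment only. If preoperative treatment counts, code it separately, because a post-surgery landmark does not fit it.
2. Make sure the dates of surgery and of first adjuvant treatment are extracted with the other chart data.
3. Analyse adjuvant OS in radically resected patients from a landmark after surgery, classified by treatment started by then. Start Kaplan-Meier, log-rank and Cox at the landmark. Keep AJCC stage and nodal involvement in the Cox model, since a landmark does not remove confounding. For DFS, do the same among patients recurrence-free at the landmark.
4. Choose the landmark from the distribution of start dates before outcomes are analysed. Alternatively, or as a sensitivity analysis, use a time-dependent adjuvant covariate.
5. In the whole-cohort Cox model, make adjuvant therapy time-dependent or leave it out, and code resection as time-dependent where surgery follows diagnosis. Changing resection alone makes the adjuvant bias worse (HR 0.80, 30% false positives, under the assumptions above with surgery always after diagnosis).

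**Cost.** Two dates per chart for up to 400 charts within the April-May 2024 collection period, plus a definition and a paragraph of analysis text. Under the assumptions, about 15 of 270 resected patients die or are censored before a 3-month landmark and leave that analysis. Late starters count as untreated, which dilutes a true effect. If starts are spread evenly over 2-4 months, a 3-month landmark misses (4 − 3)/(4 − 2) = half of the treated patients, and a 2-month landmark has none. This is why the landmark should follow the observed start dates.

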## **3. Study endpoint**

3.1 Primary endpoints: Median overall survival, 3 - and 5-year overall survival rates for the cohort

3.2 Secondary endpoints: overall survival with adjuvant therapy, pancreatic invasion, and advanced tumor

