## **4. Study design**

This retrospective analysis was designed to clarify long-term survival outcomes in patients diagnosed with non-ampulla DA. The study spans a 15-year period, from 2009 to 2023, capturing a comprehensive dataset that reflects advancements in diagnostic and treatment strategies over time. This cohort of 400 patients was carefully selected to provide a robust data set for analyzing survival outcomes and identifying prognostic factors affecting overall survival (OS) and disease-free survival (DFS).

No randomized or any protocol-driven treatment will be administered or provided to the subjects during the study. If clinically applicable, treatment decisions and treatment options are made at the discretion of the treating physician.

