## **5. Study population**

The patients included in this study were diagnosed and treated in the Department of General Surgery of Nanfang Hospital, Southern Medical University. Inclusion criteria are histologically confirmed non-ampulla DA includes all stages of disease at diagnosis.

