## 5.2 Inclusion criteria:

- (1) At least 18 years of age;
- (2) Voluntarily sign informed consent;
- (3) Non-ampulla DA patients were diagnosed according to the Guidelines for Clinical Diagnosis and Treatment of Gastrointestinal Tumors of the Chinese Medical Association (2022 edition), including patients at all stages of diagnosis;
- (4) Unless there are no other malignant tumors in the ampulla other than DA.

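### The only DFS rule, on its likelier reading, does not count death as an event, and nothing limits DFS to resected patients in an all-stage cohort

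*Combined protocol and SAP*

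**What the plan says.** One sentence in the Summary of research scheme (statistical analysis row) carries both time-to-event definitions. Its first half reads "Survival outcomes, including OS and DFS, were calculated from the date of diagnosis until the date of death or last follow-up"; its second half reads "from the date of diagnosis until the date of disease recurrence or last follow-up of DFS". No other section defines DFS. Section 4 gives one purpose of the data set as "identifying prognostic factors affecting overall survival (OS) and disease-free survival (DFS"), and section 10.1 repeats that aim. Sections 10, 10.2 and 10.3 cover software, group comparisons and the significance level, and add no DFS rule.

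On population, section 5 states "Inclusion criteria are histologically confirmed non-ampulla DA includes all stages of disease at diagnosis", and section 5.2 says "including patients at all stages of diagnosis". The Cox covariates in the Summary include "treatment details (radical resection, adjuvant therapy") and the pathological findings "AJCC stage, tumor differentiation and lymph node involvement rate". No section names a separate analysis set for DFS.

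The primary endpoint in section 3 is "Median overall survival, 3 - and 5-year overall survival rates for the cohort". The secondary endpoints there are also OS. Section 6.4 lists length of survival, recurrence and operative details among the data to be extracted.

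**The concern.** DFS is meant to describe how long patients who have been made free of disease stay alive and free of it. Two features of the plan work against that.

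- **Event.** If the second half of the sentence is the DFS rule, a patient who dies without recorded recurrence leaves the curve as if still disease-free and merely unobserved.
- **Population.** An all-stage cohort will contain patients who were never resected and so never disease-free. Recurrence has no clear meaning for them, and the plan does not say whether persistent disease or progression counts as an event.

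At stake are the DFS curves and the analysis of prognostic factors for DFS, including any contrast by radical resection. The main objective asks about resection and OS, so a DFS contrast driven by coding could sit beside the OS result in the same report and confuse its reading.

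**Working it through.** **1. Reading the rule.** Taken in order, the two halves of the sentence give OS (diagnosis to death) and then DFS (diagnosis to recurrence). The opening words name both outcomes, so a reading in which death ends both cannot be excluded. That reading is strained, because OS would then have no definition of its own.

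**2. Direction for omitted deaths.** Assume that a patient who dies without recurrence is censored at the date of death. Each patient then leaves the risk set at the same time under either rule. At a time with n at risk, e recurrences and m deaths without recurrence, the Kaplan-Meier factor is 1 - e/n with death censored and 1 - (e+m)/n with death counted. The first is never smaller, so the curve with death censored is never lower, and it is higher after the first such death. A check on 500 simulated cohorts of 400 found no exception (assumed: 30% unresected with median survival 1 year and no recurrence; r = 50%, d = 20% in resected patients; censoring uniform over 0.5-15 years).

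**3. Size in resected patients.** The documents give no recurrence or death rates, so r and d are assumptions, taken as independent. The plan names no DFS time point; 5 years is borrowed from OS.

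- Written rule: 1 - r
- Death counted: (1 - r)(1 - d)
- Excess: (1 - r)d

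| r | Written rule | Excess, d=5% | d=10% | d=20% | d=30% |
|---|---|---|---|---|---|
| 40% | 60% | 3.0 | 6.0 | 12.0 | 18.0 |
| 50% | 50% | 2.5 | 5.0 | 10.0 | 15.0 |
| 60% | 40% | 2.0 | 4.0 | 8.0 | 12.0 |

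Excess is in percentage points; the range is 2-18.

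**4. Would renaming the curve help?** Calling it recurrence does not repair it. With constant hazards h = -ln(1-r)/5 for recurrence and g = -ln(1-d)/5 for death, the 5-year cumulative incidence of recurrence is [h/(h+g)] × [1 - (1-r)(1-d)].

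| r, d | 1 minus Kaplan-Meier | Cumulative incidence |
|---|---|---|
| 40%, 10% | 40% | 38.1% |
| 40%, 20% | 40% | 36.2% |
| 50%, 10% | 50% | 47.7% |
| 50%, 20% | 50% | 45.4% |

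Read as recurrence risk, the curve is 1.9-4.6 points too high.

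**5. Direction of a comparison by resection.** Suppose unresected patients enter the DFS set and death is not an event.

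- If neither progression nor persistent disease is coded, unresected patients have 0 observed events. Their log-rank expected count is above 0 once any resected patient recurs while an unresected patient is at risk. The contrast points against resection.
- If persistent disease is coded as an event at diagnosis, with an assumed 30% unresected (120 of 400), 120 events are observed against 120 × 120/400 = 36 expected. The contrast points towards resection.

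Recording progression in some unresected patients falls between these two cases, and the documents give no share. The sign is therefore set by a coding rule that the plan does not state.

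**6. Clock start.** In resected patients, time from diagnosis to resection is event-free by construction. With constant hazard and a gap of x years, starting at diagnosis raises 5-year DFS by S(5-x) - S(5), where S(5-x) = S(5)^((5-x)/5). For assumed S(5) of 0.40-0.54 and x of 1-3 months this is 0.6-1.9 points. For example, S(5) = 0.40 and x = 0.25 give 0.40^0.95 - 0.40 = 0.419 - 0.400.

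**The case against.** The strongest reply has four parts.

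- **No listed endpoint depends on DFS.** Objectives and endpoints are OS only, and sections 4 and 10.1 mention DFS in a single clause each. This stands and limits the weight of the point. DFS is still calculated under the Summary and named as an outcome for prognostic factors, so it needs a workable definition.
- **The sentence may be a translation slip.** Possibly so, and death may have been intended for both outcomes. But nothing elsewhere corrects it, and two analysts could code the same deaths differently. The population gap exists on either reading.
- **The size is a choice of inputs.** This stands. The excess is proportional to d, and at d = 5% it is only 2-3 points. Only the direction is independent of assumptions about rates.
- **Incomplete records and missing diagnostic or treatment data are excluded.** That may remove some unresected patients, for instance those without nodal data, and makes the effect in a multivariable DFS model hard to predict. It does not remove unresected patients with complete records, and it does not define a DFS set.

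A reader might infer more: that a DFS log-rank test would almost surely show resection to be harmful. The documents do not support this. It needs unresected patients in the DFS set, death not counted, exactly no progression or persistent disease coded as an event, and a test by resection, which the plan does not name (it refers only to patient subgroups). Recording progression in even a modest share of unresected patients can remove or reverse the result, so no rejection percentage should be quoted.

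**Conclusion.** The point holds. On the likelier reading, the only DFS rule censors deaths without recorded recurrence and biases Kaplan-Meier DFS upward. The size at 5 years is about 2-18 points, resting wholly on assumed r of 40-60% and d of 5-30%. Independently of that reading, the DFS population and the coding of persistent disease and progression are undefined, so a DFS contrast by resection has no determinate direction.

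The defect is confined to DFS. It would be wrong to infer that the primary or secondary results are compromised: those are OS, and their definition counts death. The change should be made, but the study's main conclusion does not hang on it. Confidence is medium, because the sentence is ambiguous.

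**What to change.** In the statistical analysis row of the Summary, and preferably also in section 10.2:

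1. Define DFS as time to the first of recurrence or death from any cause, censored at last follow-up if neither has occurred.
2. Analyse DFS only in radically resected patients, with that term defined in the plan, and omit radical resection from the DFS model.
3. Label DFS exploratory, since section 3 does not list it.
4. Start the DFS clock at resection if that date can be extracted. Otherwise keep diagnosis and state that the interval before resection is event-free by construction.
5. If recurrence alone is wanted, name it time to recurrence and report cumulative incidence with death as a competing event.

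The cost is mainly wording, plus a check that dates of recurrence and death are extracted. Section 6.4 covers survival and recurrence but names no resection date, although the operative details may include it. Item 5 also needs a check that the named software produces cumulative incidence. Reported DFS will be lower, and its population smaller: 240-360 patients if 60-90% of the 400 were resected (400 × 0.6 and 400 × 0.9; the share is assumed).

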#### 6.4 Data Collection Procedure

- (1) Record demographic data: date of birth, gender, initials;
- (2) Medical history and physical examination (including vital signs, height, weight, BMI, physical examination of all systems; HCC history Present history, etiology)
- (3) Clinical presentation (symptoms, tumor location, stage of diagnosis), treatment modalities (surgical intervention, adjuvant therapy) and survival outcome (survival time, recurrence), details of surgical procedure (resection extent, lymph node dissection);
- (4) Record laboratory test results: including preoperative laboratory values (such as CEA, CA19-9 levels) and available genetic markers Markers (KRAS mutation, dMMR/MSI-H);
- (5) Pathological findings (tumor differentiation, lymphatic vascular infiltration, perineural infiltration) were recorded.

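### Treatment was discretionary, but fitness is neither a named data item nor a Cox covariate: the resection association is probably exaggerated, and the adjuvant estimate is biased in an uncertain direction.

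*Combined protocol and SAP*

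**What the plan says.** The main objective is a treatment contrast: "To determine whether radical DA resection is associated with an improvement in 5-year overall survival". Section 2.2 adds adjuvant therapy as a second treatment factor: "Adjuvant therapy, pancreatic invasion, and advanced tumor stage were identified as significant predictors of overall survival". Section 4 rules out randomization and says that "treatment decisions and treatment options are made at the discretion of the treating physician".

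The statistical analysis row of the summary describes Kaplan-Meier curves, log-rank tests and Cox models. On the Cox models it says: "Variables considered in the model included demographic factors (age, sex), clinical features (BMI, jaundice, bleeding, anemia), preoperative laboratory values". It then adds radical resection, adjuvant therapy and "pathological findings (AJCC stage, tumor differentiation and lymph node involvement rate".

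Section 6.4(2) collects "Medical history and physical examination (including vital signs, height, weight, BMI, physical examination of all systems; HCC history" and further history. It names no performance status, ASA grade or comorbidity measure. Neither the summary nor section 10 describes matching, weighting, a propensity score or a sensitivity analysis for unmeasured confounding.

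The background (section 1) says of earlier retrospective comparisons of surgery with and without additional treatment, "so there may be selection bias in patients". It then sets out to separate the effects of tumor characteristics, surgery and adjuvant therapy.

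**The concern.** Fitness plausibly influences both whether a patient is offered major surgery (section 1 notes that this is often pancreaticoduodenectomy) and how soon the patient dies. That makes it a confounder of the resection contrast, and the same argument applies to adjuvant therapy after an operation. The covariate list mainly describes the tumor and its presentation. Adjusting for stage, differentiation and nodes makes groups more alike in their disease, but does little to make them alike in general health.

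The treatment hazard ratios are at stake. If unfit patients are concentrated in the unresected group, part of their excess mortality will be credited to resection, and a reader of the report could not tell how much.

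**Working it through.** **1. Can any planned figure be reproduced?** No. The only design figure is 400 patients, given without effect size, power, event count or treatment split. The point does not depend on it.

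**2. Data items against model terms**

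| Domain | Collected (6.4) | In the Cox list (summary) |
|---|---|---|
| Age, sex, BMI | yes | yes |
| Laboratory values | yes | yes |
| Medical history | yes, uncoded | no |
| Performance status, ASA grade, comorbidity index | not named | no |
| Stage, differentiation | yes | yes |
| Lymphovascular and perineural infiltration | yes | no |
| Pancreatic invasion | not named | no |

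**3. Possible size for fitness alone.** For an unmeasured binary factor, approximately:

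HR observed = HR true × [1 + p1(g − 1)] / [1 + p0(g − 1)]

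Here p1 and p0 are the proportions unfit among treated and comparator patients, and g is the hazard ratio for death in unfit patients. None of these is in the documents; all values are assumptions. The formula also treats fitness as unrelated to the listed covariates, so it shows the bias before any absorption by proxies. With p1 = 10%:

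| p0 | g = 1.5 | g = 2.0 | g = 2.5 |
|---|---|---|---|
| 20% | 1.05/1.10 = 0.955 | 1.10/1.20 = 0.917 | 1.15/1.30 = 0.885 |
| 30% | 1.05/1.15 = 0.913 | 1.10/1.30 = 0.846 | 1.15/1.45 = 0.793 |
| 40% | 1.05/1.20 = 0.875 | 1.10/1.40 = 0.786 | 1.15/1.60 = 0.719 |

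A true hazard ratio of 1.0 would appear as about 0.95 (1.05/1.10 = 0.9545) to 0.72. In the middle case (10% versus 30%, g = 2.0) it would appear as about 0.85.

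**4. Adjuvant therapy: an opposing bias.** Section 1 says adjuvant therapy has been explored especially where pathology is adverse. Stage, nodes and differentiation are in the Cox list, but the last two rows of the table in step 2 are not. Suppose such residual adverse pathology is commoner in treated patients (assumed inputs again, same formula):

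- 50% versus 30%, hazard ratio 1.5: 1.25/1.15 = 1.087
- 60% versus 30%, hazard ratio 2.0: 1.60/1.30 = 1.231
- 50% versus 20%, hazard ratio 2.0: 1.50/1.20 = 1.250

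Multiplying by the fitness factor gives the net effect:

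- 0.846 × 1.087 = 0.92
- 0.955 × 1.087 = 1.04
- 0.846 × 1.231 = 1.04
- 0.955 × 1.250 = 1.19

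The net factor falls on either side of 1, so its direction cannot be fixed from the documents.

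**The case against.** The strongest reply is that the model is not blind to fitness. Age, BMI, anemia and preoperative laboratory values are all plausible proxies, and to the extent that they track fitness the Cox model removes part of the bias. Medical history and a full examination are collected, so comorbidity is at least partly recoverable. The summary says the variables included those listed, which need not be exhaustive. All of this stands. It means the figures above overstate what would remain after adjustment, and that a reader who infers that the plan can do nothing about confounding by fitness goes too far. It does not supply a prespecified fitness term, and partial proxies leave a residual.

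A second reply concerns reach. The primary endpoints in section 3.1 are whole-cohort median, 3-year and 5-year survival, which this confounding does not touch. The main objective is worded as an association, and the Cox model is meant to find prognostic factors. That also stands. The point is limited to the treatment hazard ratios and to the causal reading invited by the background's aim of separating the effects of surgery and adjuvant therapy.

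Third, the selection-bias remark in section 1 concerns surgery alone against surgery with additional treatment. It should not be read as an admission about resected and unresected patients.

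**Conclusion.** The omission is real. Treatment was discretionary, fitness is neither a named data item nor a Cox covariate, and no other control for confounding by indication is planned. For resection, residual confounding probably exaggerates the association. The direction rests on the clinical presumption that unfit patients are resected less often and die sooner. The illustrative size is a factor of about 0.95 to 0.72 on assumed inputs, less whatever the proxies absorb.

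A reader might infer that both treatment effects are overstated. The documents do not support that. They contain no fitness data by treatment group, so even for resection the word is probably. For adjuvant therapy, fitness alone pushes toward apparent benefit while adverse pathology pushes the other way, and the illustrative net factor runs from 0.92 to 1.19. That uncertainty is itself a reason to measure fitness, since the adjuvant hazard ratio is hard to interpret without it.

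This is a worthwhile and inexpensive improvement to the treatment comparisons. It does not invalidate the cohort survival estimates.

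**What to change.** - **Data (section 6.4(2)).** Code a comorbidity index for every patient from the medical history already collected. Abstract performance status at diagnosis where it is charted.
- **Model.** Force the comorbidity index into the Cox models for resection and for adjuvant therapy. Enter performance status as a separate covariate, with multiple imputation or a sensitivity analysis in patients with a charted value. Do not substitute one measure for the other patient by patient, which would mix two constructs in one term.
- **ASA grade.** Use it only in the adjuvant comparison among operated patients. If recorded only for operated patients, it cannot adjust resected against unresected.
- **Eligibility.** State that missing performance status or ASA grade does not trigger the incomplete-records exclusion (summary and section 5.3). Records go back to 2009, and otherwise the new fields could shrink the cohort.
- **Reporting.** Give both treatment hazard ratios with and without the fitness adjustment.

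The cost is a few extra fields from charts already being read and one or two more model terms. Performance status will be missing in some older records, and the resection benefit will probably look smaller.
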